9.3 Study Calendar – Phase II D+T+G (contd.)

			Сус	le 1			Cyc	cle 2			Cyclo	e 3 + β		Follow-Up Prior to Progression	At Time of Progression	Post- Progression Follow Up Ψ
REQUIRED STUDIES	PRE-	Wk	Wk	Wk	Wk	Wk	Wk	Wk	Wk	Wk	Wk	Wk	Wk			
OTOBIES	STUDY	1	2	3	4	5	6	7	8	9	10	11	12			
X-RAYS & SCANS																
CT or MRI Scan of the brain	Х															
CT or MRI ¥	X									Х				X£	Х	
ECHO or MUGA	Х									Χπ						
ECG	Х															
SPECIMEN SUBMISSION																
Paraffin-Embedded Tissue/Slides (Fresh Frozen Tissue																
If Available)	Х			ΧФ											X	
Plasma and Buffy Coat ®	Х									Х					X	
TREATMENT																
Dabrafenib ∑		Х	Х	Х	Х	Х	Х	Х	Х	Х	Х	Х	Х			
Trametinib -		X	X	Х	X	Х	X	X	X	Х	Х	X	X			
GSK2141795 r		Х	Х	Х	Х	Х	Х	Х	Х	Х	Х	Х	Х			

Click here for footnotes.

NOTE: Forms are found on the protocol abstract page of the SWOG website (www.swog.org). Forms submission guidelines are found in Section 14.0.

Footnotes:

- ¥ Disease assessments must be performed after every two cycles of treatment using the same method as baseline and must be documented on the Follow-Up Tumor Assessment Form (RECIST 1.1). A response must be confirmed by a second determination at least 4 weeks after a complete or partial response has been noted.
- \sqrt{V} Ophthalmic exam must be performed at baseline. Follow-up exams are to be performed as clinically indicated.
- ** Dermatology exams are required every 2 months throughout treatment, and every 2 months through 6 months after discontinuation of dabrafenib or until the start of another anti-neoplastic therapy.
- π On treatment echocardiogram should be obtained every 2 months for all patients.
- ☐ Patients known to be HIV + must not be on antiviral agents and must have CD34 counts ≥ 500 mm³ (see Section 5.1t).
- Δ See Sections 5.1u and 7.2b.
- B Protocol treatment assessments will continue on this schedule until any one of the criteria in Section 7.8 is met.
- £ Once off protocol treatment, disease assessments must be performed every 8 weeks until disease progression.
- Ψ After disease progression (see Section 10.2), follow-up for survival status must be performed every 3 months for the first year, then every 6 months for a total of 3 years from the date of registration or death, whichever is first.
- ≠ Assessments should continue until resolution of all acute adverse events. Patients with AEs at progression should be followed at frequencies appropriate for the nature and duration of the events, until the AE has resolved or is deemed irreversible.
- \sum To be taken twice daily.
- To be taken once a day.
- Ω For melanoma patients only.
- Required at baseline and prior to dosing on Days 15 and 29. Three patients treated within the second cohort of the Phase I Portion (D+T+G) will have more extensive PK sampling at baseline, pre-dose and +1, +2, +4, and +8 hours on Day 15, and pre-dose Day 29.
- Φ Optional biopsy between Day 15-28.
- ® Plasma and buffy coat must be submitted at baseline, before the start of Cycle 3 and at the time of progression.
- + As clinically indicated to evaluate adverse events (i.e., abdominal pain, pancreatitis, etc).

10.0 CRITERIA FOR EVALUATION AND ENDPOINT DEFINITIONS

- 10.1 Measurability of Lesions
 - a. Measurable disease: Measurable disease is defined differently for lymph nodes compared with other disease and will be addressed in a separate section below.
 - 1. Lesions that can be accurately measured in at least one dimension (longest diameter to be recorded) as ≥ 2.0 cm by chest x-ray, by ≥ 1.0 cm with CT or MRI scans, or ≥ 1.0 cm with calipers by clinical exam. All tumor measurements must be recorded in decimal fractions of centimeters (or millimeters).

The defined measurability of lesions on CT scan is based on the assumption that CT slice thickness is 0.5 cm or less. If CT scans have slice thickness greater than 0.5 cm, the minimum size for a measurable lesion should be twice the slice thickness.

- 2. Malignant lymph nodes are to be considered pathologically enlarged and measurable if it measures ≥ 1.5 cm in **SHORT AXIS** (greatest diameter perpendicular to the long axis of the lymph node) when assessed by scan (CT scan slice recommended being no greater than 0.5 cm).
- b. Non-measurable disease: All other lesions (or sites of disease), including small lesions (longest diameter < 1.0 cm or pathologic lymph nodes with ≥ 1.0 cm to < 1.5 cm short axis), are considered non-measurable disease. Bone lesions, leptomeningeal disease, ascites, pleural/pericardial effusions, lymphangitis cutis/pulmonitis, inflammatory breast disease, and abdominal masses (not followed by CT or MRI), are considered non-measurable as are previously radiated lesions that have not progressed.

c. Notes on measurability

- For CT and MRIs, the same type of scanner should be used and the image acquisition protocol should be followed as closely as possible to prior scans. Body scans should by performed with breath-hold scanning techniques, if possible.
- 2. PET-CT: At present, the low dose or attenuation correction CT portion of a PET-CT is not always of optimal diagnostic CT quality for use with RECIST measurements. However, if the site can document that the CT performed as part of a PET-CT is of identical diagnostic quality to a diagnostic CT, then the CT portion of the PET-CT can be used for RECIST measurements and can be used interchangeably with conventional CT.
- 3. Ultrasound: Ultrasound is not useful in assessment of lesion size and should not be used as a method of measurement.
- 4. Cystic lesions that meet the criteria for radiographically defined simple cysts should not be considered as malignant lesions (neither measurable nor non-measurable) since they are, by definition simple cysts.
- 5. If a target lesion becomes very small some radiologists indicate that it is too small to measure. If the lesion is actually still present, a default measurement of 0.5 cm should be applied. If the radiologist believes the lesion has gone, a default measurement of 0.0cm should be recorded.

10.2 Objective Status at Each Disease Evaluation

Objective Status is to be recorded at each evaluation. All measurable lesions up to a maximum of 2 lesions per organ 5 lesions in total, representative of all involved organs, should be identified as target lesions at baseline. All other lesions (or sites of disease) including any measurable lesions over and above the 5 target lesions should be identified as non-target lesions. Measurements must be provided for target measurable lesions, while presence or absence must be noted for non-target measurable and non-measurable disease.

For studies that use disease progression as an endpoint, whole body scanning at specific intervals is necessary to determine that progression is NOT present outside of the "target" areas. Therefore, in these studies it is not acceptable to image only the "target" areas of the body in follow-up scans. For study-specific imaging requirements, see the Study Calendar in Section 9.0.

- a. Complete Response (CR): Complete disappearance of all target and non-target lesions (with the exception of lymph nodes mentioned below). No new lesions. No disease related symptoms. Any lymph nodes (whether target or non-target) must have reduction in short axis to < 1.0 cm. All disease must be assessed using the same technique as baseline.
- b. Partial Response (PR): Applies only to patients with at least one measurable lesion. Greater than or equal to 30% decrease under baseline of the sum of appropriate diameters of all target measurable lesions. No unequivocal progression of non-measurable disease. No new lesions. All target measurable lesions must be assessed using the same techniques as baseline.
- Stable: Does not qualify for CR, PR, Progression or Symptomatic Deterioration.
 All target measurable lesions must be assessed using the same techniques as baseline.
- d. Progression: One or more of the following must occur: 20% increase in the sum of appropriate diameters of target measurable lesions over smallest sum observed (over baseline if no decrease during therapy) using the same techniques as baseline, as well as an absolute increase of at least 0.5 cm. Unequivocal progression of non-measurable disease in the opinion of the treating physician (an explanation must be provided). Appearance of any new lesion/site. Death due to disease without prior documentation of progression and without symptomatic deterioration (see Section 10.2e).

Notes regarding new lesions: FDG-PET imaging can complement regular scans in identifying new lesions according to the following algorithm.

- 1. Negative FDG-PET at baseline, with a positive FDG-PET at follow-up is a sign of progression based on a new lesion.
- 2. No FDG-PET at baseline and a positive FDG-PET at follow-up corresponding to a potential new site of disease must have a confirmation by anatomical assessment (e.g., CT, MRI, x-ray) as new site of disease to be considered progressive disease. In such a case, the date of progressive disease will be the date of the initial abnormal FDG-PET.
- e. Symptomatic deterioration: Global deterioration of health status requiring discontinuation of treatment without objective evidence of progression. Efforts should be made to obtain objective evidence of progression after discontinuation.

f. Assessment inadequate, objective status unknown. Progression or symptomatic deterioration has not been documented, and one or more target measurable lesions have not been assessed or inconsistent assessment methods were used.

g. Objective status notes:

- 1. Non-measurable and non-target measurable disease do not affect Objective Status in determination of CR (must be absent--a patient who otherwise has a CR, but who has non-measurable or non-target measurable disease present or not assessed, will be classified as having a PR). However, non-measurable and non-target lesions are included in determination of progression (if new sites of disease develop or if unequivocal progression occurs in the opinion of the treating physician).
- 2. An objective status of PR or stable cannot follow one of CR. Stable can follow PR only in the rare case that tumor increases too little to qualify as progression, but enough that a previously documented 30% decrease no longer holds.
- 3. In cases for which initial flare reaction is possible (hypercalcemia, increased bone pain, erythema of skin lesions), objective status is not progression unless either symptoms persist beyond 4 weeks or there is additional evidence of progression.
- 4. Lesions that appear to increase in size due to presence of necrotic tissue will not be considered to have progressed.
- For bone disease documented on bone scan only, increased uptake does not constitute unequivocal progression. However, increase in the soft tissue component of a lesion as measured by CT or MRI would constitute progression.
- 6. Appearance of new pleural effusions does not constitute unequivocal progression unless cytologically proven of neoplastic origin, since some effusions are a toxicity related to therapy or other medical conditions. Increase in the size of an existing effusion does not constitute unequivocal progression, since the fluid status of the patient could alter the size of the effusion.
- 7. If CR determination depends on a lesion for which the status is unclear by the required tests, it is recommended the residual lesion be investigated with biopsy or fine needle aspirate.

10.3 Best Response

This is calculated from the sequence of objective statuses.

- a. CR: Two or more objective statuses of CR a minimum of four weeks apart documented before progression or symptomatic deterioration.
- b. PR: Two or more objective statuses of PR or better a minimum of four weeks apart documented before progression or symptomatic deterioration, but not qualifying as CR.
- c. Unconfirmed CR: One objective status of CR documented before progression or symptomatic deterioration but not qualifying as CR or PR.

- d. Unconfirmed PR: One objective status of PR documented before progression or symptomatic deterioration but not qualifying as CR, PR or unconfirmed CR.
- e. Stable/no response: At least one objective status of stable/no response documented at least 6 weeks after registration and before progression or symptomatic deterioration, but not qualifying as anything else above.
- f. Increasing disease: Objective status of progression within 12 weeks of registration, not qualifying as anything else above.
- g. Symptomatic deterioration: Objective status of symptomatic deterioration within 12 weeks of registration, not qualifying as anything else above.

Inadequate assessment, response unknown: Progression or symptomatic deterioration greater than 12 weeks after registration and no other response category applies.

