7.9 Criteria for Removal from Protocol Treatment

- a. Progression of disease as defined in Section 10.2d. However, the patient may continue to stay on protocol treatment as long as in the opinion of the treating investigator the patient is continuing to clinically benefit from treatment. This may be if there are lesions that continue to respond to the therapy despite others progressing, or if there is symptomatic relief of symptoms on therapy.
- b. Symptomatic deterioration (as defined in Section 10.2e).
- c. Unacceptable toxicity.
- d. Treatment delay of both protocol drugs for any reason > 8 weeks.
- e. The patient may withdraw from the study at any time for any reason.

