11.3 Evaluation of Dabrafenib + Trametinib + GSK2141795 (D+T+G)

a Analysis of Phase I Portion

Section 7.4 provides the details of the study design for the Phase I Portion of the study. The Phase I Portion will be a limited dose-escalation.

The primary objective of the Phase I Portion will be to determine the maximum tolerated dose (MTD) of GSK2141795, dabrafenib and trametinib in patients with BRAF mutant locally advanced or metastatic cancer. The regimen will be considered safe and the MTD determined if the dose-limiting toxicity rate is \leq 33%.

Prior to implementation of the Phase II Portion, a temporary closure will occur in order to assess dose and to evaluate the safety profile more fully.

b Analysis of Phase II Portion

The study will be conducted in two sequential parts. Patients enrolled to the Phase I Portion will not be included in the analysis of the Phase II Portion.

The primary objective of this portion study is to evaluate the objective response rate (confirmed and unconfirmed, complete and partial responses) of GSK2141795 used in combination with dabrafenib and trametinib in patients with Stage IV or unresectable Stage III melanoma who have acquired resistance to BRAF inhibitor-based therapy. Resistance to BRAF inhibitor-based therapy will be defined as progressive disease by RECIST 1.1 criteria while receiving therapy with a BRAF inhibitor (vemurafenib or dabrafenib, alone or in combination with a MEK inhibitor). This may be innate resistance (patients who never achieved a tumor response while on BRAF inhibitor therapy) or acquired resistance (progression after having a tumor response to BRAF inhibitor therapy).

It is assumed that this regimen will not be of further interest if the true response rate is less than 15% (null) and that a true response rate of 35% or more would be of considerable interest for further investigation (alternative).

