- 2. You are associated as an investigator or CRA/RN at the institution where the patient is being treated or followed,
- 3. Your Web User Administrator has added you as a web user and has given you the appropriate system permissions to view data for that institution.

For assistance with points 1 and 2 call the Operations Office at [name]. For point 3, contact your local Web User Administrator (refer to the "Who is my Web User Administrator?" function on the swog.org Members logon page).

For difficulties with the CRA Workbench, please email technical [contact].

- 14.4 Data Submission Overview and Timepoints
 - a. WITHIN 7 DAYS OF REGISTRATION FOR ALL PATIENTS SUBMIT:

S1221 Onstudy Form

Baseline Tumor Assessment Form (RECIST 1.1)

\$1221 Baseline Abnormalities Form

Radiology reports from all scans performed to assess disease at baseline

Pathology report from a CLIA certified lab documenting BRAF mutation status

ALSO SUBMIT WITHIN 7 DAYS OF REGISTRATION FOR PATIENTS ENROLLED ON THE PHASE II PORTION:

Pathology report documenting histologic confirmation of malignant melanoma.

b. SUBMIT WITHIN 14 DAYS AFTER REGISTRATION:

Pre-study specimens as outlined in Section 15.4.

c. WITHIN 7 DAYS AFTER COMPLETION OF EVERY CYCLE (1 CYCLE = 28 DAYS), SUBMIT:

\$1221 Treatment Form

S1221 Adverse Event Form (Submit every 14 days during Cycles 1 and 2 of Phase I Portion, see Section 15.1 for Rapid Reporting requirements):

d. WITHIN 7 DAYS AFTER EVERY TUMOR ASSESSMENT (INCLUDING BOTH ON TREATMENT AND OFF TREATMENT PRIOR TO DISEASE PROGRESSION) (see Section 9.0 for Disease Assessment Schedule) SUBMIT:

Follow-Up Tumor Assessment Form

Radiology reports from all scans performed to assess disease. Physician must note tumor measurement in patient records.

e. WITHIN 14 DAYS OF PROGRESSION SUBMIT:

NOTE: IF PATIENT REMAINS ON TREATMENT FOLLOWING PROGRESSION (SEE SECTION 7.9a, CONTINUE TO SUBMIT THE \$1221 ADVERSE EVENT FORM AND \$1221 TREATMENT FORM AFTER EVERY CYCLE OF TREATMENT AS OUTLINED IN SECTION 14.4c).

Follow-Up Tumor Assessment Form (RECIST 1.1)

Radiology reports from all scans performed to assess disease. Physician must note tumor measurement in patient records.

 $\underline{\textbf{S1221}}$ Treatment Form and $\underline{\textbf{S1221}}$ Adverse Event Form (if the patient was still on protocol treatment) or

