Follow-Up Form (if patient was off treatment) documenting date, site and method for determining progression.

f. WITHIN 14 DAYS OF DISCONTINUATION OF TREATMENT SUBMIT:

Off Treatment Notice

S1221 Treatment Form

\$1221 Adverse Event Form.

g. AFTER OFF TREATMENT, SUBMIT EVERY 3 MONTHS FOR 1 YEAR AND 6 MONTHS UP TO 3 YEARS FROM DATE OF REGISTRATION:

Follow-Up Form

Late Effects Form (if prior to treatment for progression or relapse or a second primary, and prior to non-protocol treatment, the patient experiences any severe [Grade \geq 3] long term toxicity that has not been previously reported).

h. WITHIN 4 WEEKS OF KNOWLEDGE OF DEATH SUBMIT:

Notice of Death **and all of the items listed in Section 14.4f** (if the patient was still on protocol treatment) or Follow-Up Form (if the patient was off protocol treatment) documenting death information.

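### Best response (Section 10.3) has no cut-off at the start of non-protocol anticancer therapy, so as written a response to a later drug can count in the D+T+G primary ORR

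*Combined protocol and SAP*

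**What the plan says.** Section 11.3b sets the Phase II primary objective: to "evaluate the objective response rate (confirmed and unconfirmed, complete and partial responses) of GSK2141795 used in combination with dabrafenib and trametinib". Section 10.3 says of best response, "This is calculated from the sequence of objective statuses". Each of its four response categories (CR, PR, unconfirmed CR, unconfirmed PR) ends at progression or symptomatic deterioration and at nothing else. The least demanding category is unconfirmed PR: "One objective status of PR documented before progression or symptomatic deterioration but not qualifying as CR, PR or unconfirmed CR".

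Section 7.9 lists reasons for leaving protocol treatment that need not involve progression, among them "Unacceptable toxicity" (7.9c) and "Treatment delay of both protocol drugs for any reason > 8 weeks" (7.9d). For such patients, footnote £ of the Phase II calendar (Section 9.3) states: "Once off protocol treatment, disease assessments must be performed every 8 weeks until disease progression". Section 14.4d collects these assessments, "INCLUDING BOTH ON TREATMENT AND OFF TREATMENT PRIOR TO DISEASE PROGRESSION".

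The protocol does use new therapy as a boundary elsewhere. Late effects (Section 14.4g) are reported only if they occur "prior to treatment for progression or relapse or a second primary, and prior to non-protocol treatment", and the post-treatment dermatology exams in Section 9.3 stop when another antineoplastic treatment starts. Sections 10.2, 10.3, 11.3 and 11.4 set no such boundary for response.

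**The concern.** The objective names the combination, but the operational rule does not require the patient to be on it, or free of other anticancer drugs, when the response is seen. Take a patient with stable disease at the week 9 scan who stops D+T+G for toxicity, starts another systemic therapy, and has a PR at a later scan before any progression. Under Section 10.3 this is an unconfirmed PR. Because unconfirmed responses count, no second scan is needed.

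The trial is single-arm and judged against fixed counts. A response credited to the wrong drug can only push the count up. It can open stage 2 or complete the 8 of 33, and no control arm would offset it. The number of patients exposed grows with the number who stop D+T+G before progression.

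**Working it through.** **1. The text.** Four statements together produce the result:
- patients may leave treatment without progression (7.9c, 7.9d);
- scans continue off treatment until progression (9.3, footnote £);
- those scans are submitted (14.4d);
- best response is taken from the whole sequence up to progression or symptomatic deterioration (10.3).

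No passage ends the sequence at a new drug.

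**2. The plan's own operating characteristics.** Inputs from Section 11.3b: null 15%, alternative 35%, 10 patients then 23 more, continue at 2 or more responses, success at 8 or more of 33. With X1 ~ Bin(10, p) and X2 ~ Bin(23, p),

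P(pass) = Σ over x = 2 to 10 of P(X1 = x) · P(X2 ≥ 8 − x).

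- p = 0.35: 0.872, which reproduces the stated 87% power.
- p = 0.15: 0.0916, or 9.2%. The stated one-sided alpha of 0.9% does not reproduce. That is a separate error and this point does not depend on it. The baseline used below is 9.2%.

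**3. Effect of miscredited responses.** Assume a share f of all patients, otherwise non-responders, leave without progression and start another therapy to which a proportion r respond. The counted rate is then 0.15 + f·r. The documents give neither f nor r. The nearest figure is in Section 2.0: a 9–15% response rate when trametinib is added after progression on dabrafenib. It is not a figure for every possible later therapy, so higher values of r are shown too.

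| f | r | Counted ORR | Expected miscredited responses in 33 (33·f·r) | P(pass) at true ORR 15% |
|---|---|---|---|---|
| 0 | – | 15.0% | 0 | 9.2% |
| 5% | 9% | 15.45% | 0.15 | 10.4% |
| 10% | 15% | 16.5% | 0.50 | 13.8% |
| 10% | 30% | 18.0% | 0.99 | 19.5% |
| 20% | 30% | 21.0% | 1.98 | 33% |

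If instead f applies equally to responders and non-responders, the counted rate is 0.15 + 0.85·f·r. The last two rows become 17.7% and 28.8%.

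**4. One miscredited patient.** This needs no f or r, but it is conditional on the event happening. Fix one patient as a counted responder and let the others respond at 15%.
- Patient in stage 1: X1 = 1 + Bin(9, 0.15), and P(pass) = 18.4%.
- Patient in stage 2: X2 = 1 + Bin(22, 0.15), and P(pass) = 15.3%.

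At stage 1, P(X1 = 1) = 10 · 0.15 · 0.85⁹ = 34.7% under the null. In about a third of such trials the count is therefore one short of the gate.

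**The case against.** The strongest reply is that the affected group is small and the intent is clear.
- Section 11.3b already describes the endpoint as the response rate of the combination, so a response to another drug lies outside what is meant.
- Sections 7.6 and 8.3 let patients continue the remaining agents when one is stopped, so many single-agent toxicities do not end protocol treatment.
- A decline in health that forces discontinuation is symptomatic deterioration (10.2e), which already closes the sequence.
- A patient who withdraws from the study (7.9e) may supply no later scans.
- These patients have already progressed on a BRAF inhibitor. Section 2.0 cites a median PFS of 3.6 months with dabrafenib plus trametinib in that setting, so many would progress early.
- A later PR must still be a fall of at least 30% below the pre-study baseline, with no new lesions.

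All of this stands as a limit on size. It does not remove the gap: the intent is not carried into the rule that classifies patients, and routes 7.9c and 7.9d remain open. A group-wide convention might cover the case, but none is stated or cited for it.

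A reader might also infer that ORR alone decides the trial, so that a poorly tolerated regimen could be declared worthwhile on other drugs' responses. The documents do not support that. Section 11.3b accepts 8 of 33 only if overall survival and adverse events also look favourable, and Section 11.4 reports discontinuations and dose delivery. That proviso is not attached to the stage 1 gate, where the count alone decides.

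**Conclusion.** The concern holds as a gap in the primary endpoint definition. Applied literally, Section 10.3 credits D+T+G with a response that first appears on a later non-protocol therapy, and the error runs in one direction only.

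Its size cannot be established from the documents. Across the assumed values, the chance of meeting the count rule at a true ORR of 15% runs from 10.4% to 33%, against 9.2% without miscrediting. The upper figure should not be read as the trial's false-positive rate: it needs a fifth of all patients to be non-responders who switch without progression and then respond at 30%. With the response rates the protocol itself cites for a related setting (9–15%) and f of 5–10%, the shift is to between 10.4% and 13.8%.

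This should be fixed before analysis. It does not by itself make the Phase II design unusable.

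**What to change.** In Section 10.3, with a reference from 11.3b, count a CR or PR (confirmed or not) only if it is documented before the earliest of progression, symptomatic deterioration, or the start of any non-protocol anticancer therapy. State that eligible patients with no qualifying status by then are non-responders and stay in the denominator.

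Make sure the start date of the first non-protocol anticancer therapy is captured. The Follow-Up Form is not in the documents, so it may already hold this date; if not, add it. Keep the off-treatment scans for PFS.

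The cost is a sentence or two of text and possibly one date field. No extra visits or patients are needed, and the two-stage design keeps its computed 9.2% alpha and 87.2% power. The reported ORR may be slightly lower.
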